Patients who participated in the prior study entitled “Prospective clinical study on serum 25-hydroxyvitamin D (25-OH D) level and risk of bronchiectasis exacerbation” (UW 22-317) will be invited for participation during regular clinic follow-up and management in Queen Mary Hospital. If they are willing to join the further research, they will be recruited in this self-controlled study. There were 104 subjects in the aforementioned study who will be separated into two groups according to their Baseline blood 25-hydroxyvitamin-D level: vitamin D deficient (below 50 nmol/L) and vitamin D non-deficient (at or above 50 nmol/L). There were initially 42 and 62 patients in the vitamin D deficient and vitamin D non-deficient groups respectively. Patients would be rechecked for 25-hydroxyvitamin-D level to confirm the persistence of deficiency at the recruitment visit.

The following eligibility criteria will apply.

Inclusion criteria: Patients with

1. ages 18 years or above, male or female.
2. confirmed diagnosis of non-CF bronchiectasis based on high-resolution computed tomography (HRCT) scan.
3. participation in the prior study entitled “Prospective clinical study on serum 25-hydroxyvitamin D (25-OH D) level and risk of bronchiectasis exacerbation” (UW 22-317)

Exclusion criteria: Patients with

1. underlying asthma, COPD and other co-existing respiratory diseases
2. underlying osteoporosis
3. supplementary Vitamin D in their regimen
4. advanced chronic kidney disease with estimated glomerular filtration rate (eGFR) < 30mL/min

7. Brief outline of methodology

The following will be performed at the recruitment visit: Detailed medical history (Demographics, duration of bronchiectasis, co-morbidities, exacerbation history), questionnaires (SGRQ, Modified Medical Research Council (mMRC) dyspnoea scale, bronchiectasis impact measure (BIM), Bronchiectasis Health Questionnaire (BHQ)), physical examination, blood tests (Complete blood count, liver and renal function test, 25-hydroxyvitamin-D level, calcium and phosphate level, erythrocyte sedimentation rate, C-reactive protein, high-sensitivity C-reactive protein), and sputum analysis (Bacterial smear and culture, acid fast bacilli smear and culture). The detailed study procedures are summarized in Table 1. The estimated duration for each visit would be 15 minutes.

Outcome measurement

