The primary outcome measure is the proportion of patients who develop hospitalized bronchiectasis exacerbation during the follow-up period of 12 months, when compared with the 1-year period before. The Vitamin D deficient group will be compared with their historical data collected in the prior study entitled “Prospective clinical study on serum 25-hydroxyvitamin D (25-OH D) level and risk of bronchiectasis exacerbation” (UW 22-317) as self-control, as well as the vitamin D non-deficient group.

The secondary outcomes include the change in SGRQ, BIM and BHQ score at 6 and 12 months from baseline, as well as change in number of all/hospitalized bronchiectasis exacerbation in the follow up period of 12 months.

Those with vitamin D deficiency will be replaced with vitamin D3 at 1000 IU at the first visit. Vitamin D3 1000 IU is expected to increase blood 25-hydroxyvitamin-D level by 25 nmol/L. Blood 25-hydroxyvitamin-D level will be rechecked 3 months after replacement. If the blood 25-hydroxyvitamin-D level is still below 50 nmol/L, the vitamin D3 replacement dosage will be increased to 2000 IU. Blood 25-hydroxyvitamin-D level will be checked again at 6 and 12 months.

Patients will be followed up at 3, 6 and 12 months after recruitment. Except for the sputum analysis and blood tests, the same measures in Table 1 will be performed at 6 and 12 months. In addition, patients will be assessed on their bronchiectasis exacerbation record (both bronchiectasis exacerbation managed in an out-patient setting and hospitalized bronchiectasis exacerbation).

Methods

Blood 25-hydroxyvitamin-D level

25-hydroxyvitamin-D will be measured in nmol/L, using in-house liquid chromatography with tandem mass spectrometry (LC/MS-MS) developed by the Department of Chemical Pathology of Queen Mary Hospital. Vitamin D deficiency is defined as 25-hydroxyvitamin-D level below 50 nmol/L, while sufficient vitamin D level is defined as above 50 nmol/L, per the Endocrine Society guidelines (32, 33).

Bronchiectasis exacerbation

Bronchiectasis exacerbation was defined as [1] a deterioration in three or more of the following key symptoms for at least 48 hours, including cough, sputum volume and/or consistency, sputum purulence, dyspnea and/or exercise tolerance, fatigue and/or malaise, hemoptysis AND [2] clinician assessment that a change in bronchiectasis treatment was required usually with administration of antibiotics treatment.

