Hospitalized bronchiectasis exacerbations are those exacerbations that fulfil the criteria above and also need at least 24 hours in-patient stay for treatment.

SGRQ

SGRQ is a disease-specific instrument designed to measure impact on overall health, daily life, and perceived well-being in patients with obstructive airway disease. Consisting of 2 parts with 50 items, it addresses frequency and severity of patients' symptoms as well as activities that cause or are limited by breathlessness. Scores range from 0 to 100, with higher scores indicating more limitations. The minimally important difference is a mean change of 4 units for slightly efficacious treatment, 8 units for moderately efficacious change and 12 units for very efficacious treatment (34, 35). SGRQ has been validated in patients with bronchiectasis and is considered a valid and sensitive instrument for determining quality of life in bronchiectasis patients (36).

BIM

Bronchiectasis Impact Measure (BIM) is another tool developed to assess patient-reported outcome in bronchiectasis. BIM is a self-administered outcome measure designed to collect patient-perceived health impact at baseline or after a follow-up period in an intervention. It was designed to address some of the perceived limitations of existing tools by being simple (eight items), giving greater scope for a range of responses (10-point visual analogue scale for each item) and by focusing on the impact of disease on quality of life rather than on the frequency or severity of symptoms. BIM consists of eight domains, namely: cough, sputum, breathlessness, tiredness, activity, general health, control, and exacerbations. A score ranges from 0 to 10 for each domain, with 10 being most severe. The total score is 80. BIM has been validated and shown to have excellent internal consistency. The domains were also shown to strongly correlate with bronchiectasis severity and exacerbation history. Statistically significant changes in all BIM domains were observed during an acute exacerbation. PI of this study translated and validated the Traditional Chinese version of BIM in year 2024.

BHQ

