BHQ was developed by Spinou et al. (37). Despite the questionnaire's simplicity, the authors concluded that the questionnaire works well in a different population from the development cohort. The instrument comprises 10 questions, each scored on a 7-point scale, to assess quality of life related to bronchiectasis on individuals for a recall period of 2 weeks. The total score ranges from 10 to 70, with a lower score indicating a more negative impact on HRQOL. PI of this study translated and validated the Traditional Chinese version of BIM in year 2024.

Table 1: Study Procedures

Visit	Study Visit			
	V1	V2	V3	V4
Months	0	3	6	12
Written informed consent	✓			
Body height, body weight and body mass index	✓			
Medical history and previous medication	✓	✓	✓	✓
Blood samples	✓	✓	✓	✓
Sputum investigation	✓			
Lung function tests	✓			
Blood pressure and pulse measurement	✓	✓	✓	✓
Physical examination	✓	✓	✓	✓
mMRC score	✓		✓	✓
SGRQ score	✓		✓	✓
BIM questionnaire	✓		✓	✓
BHQ questionnaire	✓		✓	✓
Vitamin D replacement (Only for patients with Vitamin D deficiency)	✓ (Dosage: 1000 IU)	✓ (Dosage will be increased to 2000 IU if blood vitamin D level is below 50 nmol/L)	✓	✓

Those with vitamin D deficiency will be replaced with vitamin D3 at 1000 IU at the first visit. Vitamin D3 1000 IU is expected to increase blood 25-hydroxyvitamin-D level by 25 nmol/L. Blood 25-hydroxyvitamin-D level will be rechecked 3 months after replacement. If the blood 25-hydroxyvitamin-D level is still below 50 nmol/L, the vitamin D3 replacement dosage will be increased to 2000 IU. Blood 25-hydroxyvitamin-D level will be checked again at 6 and 12 months. There are some differences from usual management to non-CF bronchiectasis subjects. The study subjects would be checked for their blood 25-hydroxyvitamin-D level during the study period. The non-CF bronchiectasis subjects with Vitamin D deficiency would be given 1000 IU and 2000 IU (if needed). We aim to correct their Vitamin D deficiency completely, aiming at blood 25-hydroxyvitamin-D level ≥ 50 , i.e. treat to target. The dose depends on the level of Vitamin D after replacement. If blood 25-hydroxyvitamin-D level is 50 or above, then 1000 IU is suffice. If blood 25-hydroxyvitamin-D level is still below 50, we will increase to 2000 IU.

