Covariates including FACED score, age, gender and smoking status will be adjusted in multivariate analysis. For secondary outcome, the change in SGRQ, BIM and BHQ scores at the end of study will be compared between the two groups by linear regression and adjusted for confounders in multivariate analysis. A p-value of <0.05 will be considered statistically significant. All the statistical analyses will be performed using the latest version of Statistical Package for the Social Sciences (SPSS) software.

8. Potential hazards to subjects in the study

Patients will undergo blood tests and breathing (lung function) tests. The breathing tests may be associated with some discomfort, such as chest soreness, shortness of breath and lightheadedness. Pain, bruising or infection may occur from the needle puncture sites. Should patients' non-CF bronchiectasis significantly worsen in the course of the study, study doctor will withdraw them from the study and provide appropriate medical treatment.

Over-replacement of Vitamin D may lead to Vitamin D toxicity which can have the following symptoms: nausea, vomiting, loss of appetite, constipation, dehydration, fatigue, irritability, confusion, weakness and/or weight loss. In this study, the blood serum 25(OH)D level will be checked before the start of Vitamin D replacement and at 3 months after replacement, to ensure the replacement is adequate but not excessive.

9. Confidentiality and use of results

The demographic and clinical data collected from study subjects will be stored securely at the study site for 5 years, with access by the principal investigator or his designated research staff. These data will only be used for the study as outlined in this protocol and individual patient's identity will be removed after completion of statistical analyses.

10. Personal experience of the investigators in the field

The Division of Respiratory Medicine has a strong track record in conducting clinical research on bronchiectasis. Queen Mary Hospital is a well-recognised tertiary referral and research centre in the field of respiratory medicine, with numerous research on bronchiectasis and respiratory diseases conducted therein during the past years. All the investigators are experienced and accredited specialist. Within the last 3 years, the PI ([name]) has served as the first author of 9 out of 10 publications on bronchiectasis.

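### No clinical-stability condition at the recruitment visit: baseline SGRQ, BIM and BHQ may be taken in or just after an exacerbation, which adds noise and could bias the secondary change scores

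*Protocol*

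**What the plan says.** Section 6 of the Protocol recruits from the prior cohort: patients "will be invited for participation during regular clinic follow-up and management in Queen Mary Hospital". There are three inclusion criteria: adult age, "confirmed diagnosis of non-CF bronchiectasis based on high-resolution computed tomography (HRCT) scan", and participation in the prior study. There are four exclusion criteria: "underlying asthma, COPD and other co-existing respiratory diseases", osteoporosis, existing vitamin D supplementation, and advanced kidney disease. None concerns a current or recent exacerbation.

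Section 7 fixes when the baseline is taken: "The following will be performed at the recruitment visit: Detailed medical history (Demographics, duration of bronchiectasis, co-morbidities, exacerbation history), questionnaires (SGRQ", followed by mMRC, BIM and BHQ. Exacerbation history is recorded at that visit, but neither entry nor the questionnaires depend on it. Table 1 repeats the questionnaires at months 6 and 12 (V3 and V4), again without a stability rule.

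On the instruments, section 7 says of BIM: "Statistically significant changes in all BIM domains were observed during an acute exacerbation". BHQ is described as designed "to assess quality of life related to bronchiectasis on individuals for a recall period of 2 weeks".

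On outcome and analysis: "The secondary outcomes include the change in SGRQ, BIM and BHQ score at 6 and 12 months from baseline", and under Data processing and analysis "the change in SGRQ, BIM and BHQ scores at the end of study will be compared between the two groups by linear regression". The covariates named there are FACED score, age, gender and smoking status. Neither the baseline score nor recent exacerbation is named.

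**The concern.** The Protocol describes a disease that runs in episodes and says that at least one of its questionnaires shifts throughout during an episode. A patient recruited in or shortly after an exacerbation gives a baseline worse than their usual state. By month 6 or 12 that patient will tend to have recovered, with or without vitamin D, and the recovery enters the change score as improvement.

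Two features could make this unequal between the groups. First, the groups are not randomised. Section 3 reports more hospitalised exacerbations over six months in deficient patients (13.3% v 2.5%), so they may be recruited near an exacerbation more often. Second, section 8 has the study doctor withdraw patients whose bronchiectasis significantly worsens. That can remove bad scores from V3 and V4, while nothing removes them from V1. Both push towards apparent benefit in the treated group.

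Eligibility and the timing of baseline measurement are protocol matters, so a separate analysis plan could not repair this after the data are collected.

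**Working it through.** The Protocol gives no figure to reproduce here. What follows is an illustration of size.

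**Inputs from the Protocol**
- Six-month proportions in the prior cohort (section 3): hospitalised exacerbation 13.3% deficient v 2.5% non-deficient; bronchiectasis exacerbation 10% v 0%.
- SGRQ total in the prior cohort (section 3): 29.3 ± 18.1 v 22.9 ± 15.2.
- Group sizes (section 6): 42 and 62, the upper limit of the pool.
- Smallest SGRQ minimally important difference (section 7): 4 units.

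**Assumptions, not in the Protocol**
- *f*: the share of a group whose V1 falls in or just after an exacerbation.
- *s*: the excess in SGRQ that later resolves, taken as 10 to 20 units, with 15 as the middle value.
- A four-week window counts as in or just after.

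SGRQ is used only because it is the one instrument with a stated threshold. The Protocol's evidence of sensitivity concerns BIM and BHQ.

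**Formulas**
- Raw change in the deficient group: false improvement = *f*D × *s*.
- Planned comparison: bias = (*f*D − *f*N) × *s*.
- If exacerbation also occurs at follow-up, each *f* becomes the share at V1 minus the share at follow-up. With equal shares at both visits the expected bias is zero. The figures below take the follow-up share as zero, so they are upper values for each scenario.

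**Raw change in the deficient group**
- 5% × 10 = 0.5 unit; 15% × 20 = 3.0 units.

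**Planned between-group comparison, *s* = 15**

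| Basis for the shares | Deficient | Non-deficient | Bias |
|---|---|---|---|
| Hospitalised events spread evenly over 26 weeks | 13.3% × 4/26 = 2.0% | 2.5% × 4/26 = 0.4% | about 0.25 unit |
| Both deficient-group figures added (23.3%) | 23.3% × 4/26 = 3.6% | 0.4% | about 0.5 unit |
| Higher shares, assumed outright | 10% | 2.5% | 7.5% × 15 = 1.1 units |

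The second row adds the two figures because the first (10%) is smaller than the hospitalised one (13.3%) and so cannot contain it. Proportions of patients miss repeat events, so the first two rows may be low. The registry cited in section 3, with about half of patients having two or more exacerbations a year, points to higher shares: one to two a year gives 1 × 4/52 = 8% to 2 × 4/52 = 15%. More extreme assumptions give more (30% v 5% with 20 units gives 5.0), but nothing in the Protocol points to such a difference between groups.

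**Against sampling error**
- SE of a between-group SGRQ difference = √(18.1²/42 + 15.2²/62) = √(7.80 + 3.73) = 3.4 units.
- This uses single-visit SDs. It also holds for a change score if the correlation between visits is 0.5. At 0.8 it becomes 3.4 × √0.4 = 2.1. Fewer participants would raise it.

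**Noise**
- Added variance at one visit = *f*(1 − *f*)*s*². At *f* = 15% and *s* = 10 this is 0.15 × 0.85 × 100 = 12.75, about 4% of 18.1² = 327.6.

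**The case against.** A reader might infer that natural recovery will show up as a treatment benefit. The documents do not support that, for three reasons. Recruitment is at regular clinic follow-up, not at acute presentation. V3 and V4 have no stability rule either, so if exacerbation is equally likely at each visit the result is noise and not bias. And the planned questionnaire analysis compares change between groups, so recovery common to both cancels. The 0.5 to 3.0 units describe a raw within-group change, which is not the stated analysis. These points stand, and they reduce the claim to a conditional one. They do not dispose of it: the withdrawal provision in section 8 gives a reason for follow-up to look milder than baseline, and the groups differ in exacerbation risk on the Protocol's own figures.

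A reader might also extend the point to the primary outcome, since an exacerbation under way at V1 could lead to an admission counted in the treated year. One such admission among 42 patients is 1/42 = 2.4 percentage points. But that error runs against treatment, every 12-month window has such a boundary, and nothing shows that an event of this kind is likely. It is not part of the finding.

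It is fair to say that some information is already collected: exacerbation history at V1, medical history and medication at every visit, and an exacerbation record at follow-up. The covariate list is also introduced as non-exhaustive. Still, history that gates nothing does not protect the baseline.

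Finally, a stability rule at V1 might seem to make the treated year start event-free. It largely does not, because the four clear weeks precede V1 and fall in the comparison year. The warning against dropping follow-up scores taken near an exacerbation is sound, because that would condition on an event the treatment is meant to prevent.

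**Conclusion.** The point holds in a limited form. The Protocol lets baseline SGRQ, BIM and BHQ be taken in or just after an exacerbation, against its own account of how BIM and BHQ behave. The near-certain consequence is some avoidable noise in the secondary change scores. A false benefit is possible in the deficient group's raw change. In the between-group comparison it also needs unequal recruitment near exacerbations, or selective withdrawal before V3 and V4.

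The documents do not determine the size. About 0.25 to 1.1 SGRQ units between groups follows from an assumed 15-unit excess, a four-week window, no offset at follow-up, and shares either derived from the six-month data or assumed at 10% v 2.5%. That is below the 4-unit threshold and well below a standard error of about 3.4. The repair is worth making because it is cheap and cannot be made after enrolment, not because the bias is shown to be large.

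**What to change.** - **Section 6:** hold V1 only when the patient has had no exacerbation, by the definition in section 7, in the previous four weeks; otherwise rebook. Four weeks is a working choice for the investigators to confirm.
- **Table 1:** at V1, V3 and V4, record yes or no for an exacerbation in the previous four weeks.
- **Data processing and analysis:** in the regression of score change, adjust for the baseline score, and for the V1 flag if anyone is enrolled outside the rule. Because the groups are not randomised and their SGRQ differed in the prior cohort (29.3 v 22.9), report the result without baseline adjustment alongside.
- **Follow-up scores:** keep all V3 and V4 scores in the main analysis and use the follow-up flag only descriptively, since exacerbation after V1 is itself an outcome.
- **Event dating:** if events are assigned by symptom onset, apply the same rule to the historical year and the treated year.

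The cost is one timing sentence, one yes/no field at three visits, and a few recruitment visits that move by some weeks. Replacement starts at V1, so rebooking moves that start too; whether this is acceptable is for the investigators to decide.

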This study therefore seeks to address the limitations in previous related studies on vitamin D replacement and bronchiectasis exacerbation occurrence through a self-controlled pilot study. We aim to investigate whether vitamin D replacement in bronchiectasis patients with vitamin D deficiency can reduce hospitalized bronchiectasis exacerbation occurrence. Patients who participated in the prior study entitled “Prospective clinical study on serum 25-hydroxyvitamin D (25-OH D) level and risk of bronchiectasis exacerbation” (UW 22-317) will be invited for participation during regular clinic follow-up and management in Queen Mary Hospital. If they are willing to join the further research, they will be recruited in this self-controlled study. There are some differences from usual management to non-CF bronchiectasis subjects. The study subjects would be checked for their blood 25-hydroxyvitamin-D level during the study period. The non-CF bronchiectasis subjects with Vitamin D deficiency would be given 1000 IU and 2000 IU (if needed). We aim to correct their Vitamin D deficiency completely, aiming at blood 25-hydroxyvitamin-D level $>= 50$, i.e. treat to target. The dose depends on the level of Vitamin D after replacement. If blood 25-hydroxyvitamin-D level is 50 or above, then 1000 IU is suffice. If blood 25-hydroxyvitamin-D level is still below 50, we will increase to 2000 IU.

4. Hypothesis

We hypothesize that replacing vitamin D to raise the blood 25-hydroxyvitamin-D level above 50 nmol/L can reduce the occurrence of hospitalized bronchiectasis exacerbation among patients with bronchiectasis and baseline vitamin D deficiency.

5. Objectives

To investigate whether vitamin D replacement in bronchiectasis patients with vitamin D deficiency can reduce hospitalized bronchiectasis exacerbation occurrence.

6. Subject recruitment

A prospective self-controlled study will be conducted to assess the potential benefits of vitamin D supplementation, aiming at raising the blood 25-hydroxyvitamin-D level above 50 nmol/L.

This study will be conducted at the Department of Medicine, Queen Mary Hospital. The Division of Respiratory Medicine at Queen Mary Hospital is a tertiary referral centre serving the entire territory and is the major receiving unit for patients with various respiratory diseases (including bronchiectasis) in the Hong Kong West Cluster.

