Patients will be followed up at 3, 6 and 12 months after recruitment. Except for the sputum analysis and blood tests, the same measures in Table 1 will be performed at 6 and 12 months. In addition, patients will be assessed on their bronchiectasis exacerbation record (both bronchiectasis exacerbation managed in an out-patient setting and hospitalized bronchiectasis exacerbation).

Subjects (with justification on the sample size)

Patients who participated in the prior study entitled “Prospective clinical study on serum 25-hydroxyvitamin D (25-OH D) level and risk of bronchiectasis exacerbation” (UW 22-317) will be recruited in this self-controlled study.

There were 104 subjects in the aforementioned study who will be separated into two groups according to their Baseline blood 25-hydroxyvitamin-D level: vitamin D deficient (below 50 nmol/L) and vitamin D non-deficient (at or above 50 nmol/L). There were initially 42 and 62 patients in the vitamin D deficient and vitamin D non-deficient groups respectively.

Data processing and analysis

The demographic and clinical data will be described in actual frequency or mean \pm SD, or median and interquartile range, where appropriate.

Baseline demographic and clinical data will be tabulated, as well as compared between Vitamin D deficient and vitamin D non-deficient groups by independent t-test or non-parametric tests where appropriate.

In the Vitamin D deficient group, the proportion of patients with hospitalized bronchiectasis exacerbation before and after vitamin D replacement will be compared by binary logistic regression. The number of all/hospitalized bronchiectasis exacerbation before and after vitamin D replacement will be compared by will be compared with linear regression.

The proportion of patients with all/hospitalized bronchiectasis exacerbation and between vitamin D deficient and vitamin D non-deficient groups will be compared by binary logistic regression. The number of all/hospitalized bronchiectasis exacerbation between vitamin D deficient and vitamin D non-deficient groups will be compared by will be compared with linear regression.

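### The primary outcome has two unranked comparators, and the deficient versus non-deficient test does not by itself answer whether vitamin D works

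*Protocol*

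**What the plan says.** In section 7 of the protocol, under Outcome measurement, the primary outcome is the proportion of patients with a hospitalized exacerbation over 12 months, "when compared with the 1-year period before". The next sentence sets the deficient group against its historical data "as self-control, as well as the vitamin D non-deficient group".

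Under Data processing and analysis, each comparison has its own test:
- The deficient group's proportions "before and after vitamin D replacement will be compared by binary logistic regression".
- The proportions "between vitamin D deficient and vitamin D non-deficient groups will be compared by binary logistic regression".

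The same section adds: "Covariates including FACED score, age, gender and smoking status will be adjusted in multivariate analysis". One threshold serves every test: "A p-value of <0.05 will be considered statistically significant".

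The design label points to the before/after contrast. Section 6 opens: "A prospective self-controlled study will be conducted to assess the potential benefits of vitamin D supplementation". The aim in section 3, repeated as the objective in section 5, is "to investigate whether vitamin D replacement in bronchiectasis patients with vitamin D deficiency can reduce hospitalized bronchiectasis exacerbation occurrence". It names no comparator.

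**The concern.** The two comparisons ask different questions. Before/after asks whether treated deficient patients changed. Deficient versus non-deficient asks whether treated patients differ, at follow-up, from patients who were never deficient and are not treated. The answers can conflict. Treated patients might improve on their own history and still do worse than the non-deficient group. They might also show no change while the group difference fails to reach significance in a small sample. The protocol does not say which pattern would meet the objective.

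The group comparison is also hard to read as evidence of efficacy, because the groups were not alike before treatment. A significant difference may only carry forward the earlier gap. A non-significant one may reflect only the sample size. At stake is what the trial may conclude from its primary outcome.

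**Working it through.** **Inputs from the protocol**
- Group sizes: 42 deficient and 62 non-deficient (section 6); 42 + 62 = 104, as stated.
- Hospitalized exacerbation at the prior study's 6-month interim analysis: 13.3% v 2.5% (section 3).
- Threshold: 0.05 per test, taken as two-sided because the protocol does not say.

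The protocol gives no power or overall error rate, so there is no figure of its own to reproduce.

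**1. Group test when vitamin D does nothing and the earlier gap persists**

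With x events among 42 and y among 62, the crude logistic (Wald) statistic is

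z = [ln(x/(42−x)) − ln(y/(62−y))] / √[1/x + 1/(42−x) + 1/y + 1/(62−y)].

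I summed the binomial probabilities of all (x, y) with |z| > 1.96. Tables with an empty cell counted as not significant.

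| Risk, deficient v non-deficient | Significant | Significant in favour of vitamin D | Not significant |
|---|---|---|---|
| 13.3% v 2.5% (6-month interim rates) | 27.7% | below 0.0001% | 72.3% |
| 25% v 5% (assumed: roughly doubled for a year) | 77.1% | below 0.0001% | 22.9% |

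A normal-approximation power formula gives about 56% for the first row. It is higher because it ignores sparse data: at 2.5%, no event occurs among 62 patients with probability 0.975^62 = 0.21, and the Wald test then cannot reach significance.

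So with no treatment effect the group test gives either a significant result against vitamin D or a non-significant result open to a caught-up reading. Neither outcome tells us whether replacement worked.

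**2. False positives if the groups had equal risk**
- Upper bound for two tests: 0.05 + 0.05 = 0.10. If independent: 1 − 0.95² = 0.0975.
- The tests share the deficient group's follow-up data. Under a normal approximation with a correctly paired before/after test, the chance that either is significant is 0.089 to 0.095 for assumed within-patient correlations of 0 to 0.7.
- If the logistic regression treats the two periods as independent, the range is 0.089 down to 0.050 over the same correlations.
- With actual binomial counts, the crude Wald tests and independent periods:

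| Common risk | Either test significant | Either significant in favour of vitamin D |
|---|---|---|
| 10% | 3.2% | 1.2% |
| 20% | 7.7% | 3.7% |
| 30% | 8.3% | 4.0% |

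The inflation is therefore modest, and absent when events are rare.

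**The case against.** **Before/after is already the lead.** The sentence that defines the primary outcome names only the year before, the study is repeatedly called self-controlled, and the objective concerns deficient patients. This stands as far as it goes: before/after is strongly implied. But the next sentence adds the second comparator with no lower rank, and no passage says which result decides.

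**A reader might infer that the trial can claim success from whichever comparison is favourable.** The documents do not support this. Given the 13.3% v 2.5% gap, a favourable significant group difference would require treated deficient patients to do significantly better than non-deficient ones, which section 1 of the working shows almost never happens without an effect. The remaining room for selective reading lies in a non-significant difference presented as catching up.

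**A reader might also count four primary p-values, crude and adjusted for each comparison.** That is inference. The protocol says covariates will be adjusted for in multivariate analysis. It does not promise separate crude and adjusted primary tests. What can be said is that it does not state which model decides.

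**Multiplicity and model choice are often left to a statistical analysis plan, and this is a single-centre pilot.** Both are fair and lower the weight of the error-rate argument. They do not remove the point. The protocol itself writes two comparators into its primary outcome, and it states an efficacy hypothesis and a significance threshold.

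**Conclusion.** The concern holds as a fault in how the protocol fixes its primary outcome: two comparators, two tests, one threshold, no ranking, and no statement of what group result would support the objective. The main harm is an unresolved conflict between two different questions. Inflation of the 5% error rate is secondary: at most about 10% in either direction under equal risks, and about 1% to 4% in the favourable direction for the crude tests.

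The 28% and 77% figures assume crude Wald logistic tests, all 42 and 62 patients analysed, and no vitamin D effect. The first also applies 6-month rates to the comparison. Actual numbers may be smaller, since participation is by invitation and deficiency is rechecked at recruitment. The interim rates rest on few patients: 70 completed that analysis, and 4/30 = 13.3% with 1/40 = 2.5% would fit that total. They should be taken as indicating the direction and rough size of the earlier gap.

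**What to change.** Under Outcome measurement in section 7:
- State that the before/after comparison of the proportion with a hospitalized exacerbation, in the treated deficient group, is the single primary analysis.
- Name in advance the one model that decides, crude or adjusted. The choice is the sponsor's, and nothing in the protocol forces either.
- Label the deficient versus non-deficient comparison supportive. Report it with estimates and confidence intervals, and make no efficacy claim from it alone. Say in advance that a non-significant difference will not be taken as evidence that the treated group has caught up.

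Match the wording under Data processing and analysis. The change takes a few sentences, needs no further data, and should be made before outcomes are examined. The sponsor gives up the option of claiming success from the group comparison.
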